5.6.15.1. Suspected HZ

A suspected case of HZ is defined as a new rash characteristic of HZ (e.g., unilateral, dermatomal and accompanied by pain broadly defined to include allodynia, pruritus or other sensations).

A diagnosis of suspected HZ will be based upon investigator or the attending physician judgment. The occurrence of suspected HZ will be reported as an AE/SAE, as appropriate. The reporting period for cases of suspected HZ will be from Day 0 to study end.

5.6.15.2. Study procedures in case of suspected HZ

The subject card will include a request to the attending physician to provide information about the clinical diagnosis of a case of suspected HZ, when contacted by the investigator or delegate. When a clinical diagnosis of suspected HZ has been made by an attending physician, the subject should ensure the study site is informed about the case.

When the investigator or delegate becomes aware that a clinical diagnosis of suspected HZ has been made by an attending physician, he/she will contact the attending physician. The investigator or delegate will obtain the relevant information from the attending physician and this information will be recorded in the HZ section or SAE and HZ section of eCRF, as applicable.

When the suspected HZ cases is self-reported, the investigator or his delegate will collect all information regarding the suspected HZ episode and this will be recorded in the HZ section or SAE and HZ section of eCRF, as applicable.

Note: Non-serious episodes of suspected HZ do not require immediate reporting to the site. The investigator/study staff will question the subject at each scheduled visit and contact regarding the onset of signs and symptoms of the suspected HZ.

Section 5.6.16. Reminder for follow-up contact

The subject/subject's LAR/caregiver will be reminded that, after Visit 2, three contacts between the subjects/subject's LAR/caregiver and the investigator and/or his delegate will take place in order to collect all relevant information on any event of interest that may have occurred (including SAEs, pIMDs, **suspected HZ** [Section 8.3], the use of concomitant medications and/or vaccinations (Section 6.6) or pregnancy [Section 8.3]), and that information will be recorded in the appropriate section of the subject's eCRF.

Section 5.6.17. Study conclusion

At the study conclusion contact, the following procedures will take place:

Recording of all **suspected HZ episodes and** SAEs (including related to study participation, or to a concurrent GSK medication/vaccine).

Section 6.5. Contraindications to subsequent vaccination

An episode of **suspected HZ** ~~at between~~ Visit 1 (Month 0, Vaccination 1) and/or Visit 2 (Month 2, Vaccination 2).

Section 8.3.1. Time period for detecting and recording adverse events, serious adverse events and pregnancies

The occurrence of suspected HZ will constitute an AE or SAE, as appropriate (and shall be reported in the HZ section of the eCRF [if an AE] or in the SAE and HZ section of the eCRF [if an SAE]). During the study, the time period for collecting and

recording of suspected HZ will range from first receipt of study vaccine to study end. When a suspected HZ episode has been reported, specific clinical information about the case, following the first vaccination visit (Month 0) until study end (Month 14), will be entered into the eCRF. Please refer to the SPM for information about recording the details of suspected HZ cases.

Table 10 Reporting periods for collecting safety information

Study activity	Pre-Vacc 1*	Visit 1 (Vacc 1)		Visit 2 (Vacc 2)		Visit 3/Month 3 phone contact (Post-vacc 2)	Month 8 phone contact SFU	Month 14# phone contact SFU
Time of reporting		Day 0/ Month 0	Day 29 post Dose 1	Day 0/ Month 2	Day 29 post Dose 2	Month 3	Month 8	Month 14#
Reporting of suspected HZ²								
Reporting of all SAEs ²								

² At pre-vaccination, suspected HZ episodes will be collected as medical history (see section 5.6.4.). Post vaccination, suspected HZ will be recorded in the diary card as an AE/SAE within the Day 0 –Day 29 period and will also be reported during the Month 3, 8 and 14 contacts.

Type	Unsolicited adverse events/SAEs, SAEs related to study participation or to GSK concomitant medication/vaccine; AEs/SAEs leading to withdrawal from the study.
Method of ‘unsolicited’ follow-up including suspected HZ	Diary cards
Method for reporting SAEs, SAEs related to study participation or to GSK concomitant medication/vaccine, Serious suspected HZ cases and pIMDs,	Electronic Expedited Adverse Events Report.
Suspected HZ cases (non serious or serious)	HZ (if an AE)/HZ and SAE (if an SAE) screen of the eCRF
AEs/SAEs leading to withdrawal from the study	AEs/SAE screen of the eCRF

Section 8.4.1. Prompt reporting of serious adverse events, pregnancies, and other events to GSK Biologicals

Note: the procedure described in this section will also apply to suspected HZ episodes qualifying as SAEs.

Section 10.8. Analysis of suspected HZ incidence was added with the wording below:

Descriptive statistics

The number of suspected HZ cases will be tabulated.

GlaxoSmithKline Biologicals SA	
Vaccines R &D Protocol Amendment 2	
eTrack study number and Abbreviated Title	204486 (ZOSTER-056)
IND number	BB-IND-13857

12.3. Requirements for Japan

Regulatory and Ethical Considerations

The study will be conducted in accordance with “the Ministerial Ordinance on the Standards for the Conduct of Clinical Trials of Medicinal Products (Ministry of Health and Welfare/Ministry of Health, Labour and Welfare Notification No.28 dated 27th March, 1997)” GCP and, Article 14-3 and 80-2 of the Pharmaceutical Affairs Law *and Evaluation and Licensing Division, Pharmaceutical Safety Bureau of MHW, Notification No. 1061, 1998.*

Study Period

The study period has not been confirmed at the time of this protocol. When needed and available, the study period can be communicated at local level, outside of this protocol.

If during the conduct of the study the HZ/su vaccine (GSK 1437173A) is approved in Japan, the study will then be locally amended to be conducted as a post-marketing study.

Voice of the Patient (VoP) Initiative

Subjects who are participating in the Zoster-056 study will be invited for a qualitative survey conducted by Polling Agency (PA) to better understand their own experience after the administration of HZ/su vaccine and what impact it may have had on their daily life, their perception of HZ/su and stated willingness to receive additional dose.

Contact details of the PA will be provided to the subjects by the investigators. Subjects who are willing to participate in this survey, can contact the PA at all stages during the study - after the first, second dose and also when full vaccination course was not completed.

Participation in the survey will be optional and will not impact subject's participation in the study.

Results of this research as well as proposal, interviews and market research material (questionnaire) are for internal use only and will not be published.

The survey is likely to elicit safety information and robust safety reporting process will be followed.

Safety reporting process:**Adverse Event (AE) Reporting:**

Any AE linked to the HZ/su vaccine reported by the interviewees must be reported by the PA to the trial investigator within 24 hours of initial receipt (or next working day if over a weekend or a national holiday).

Investigator's responsibilities are as follows:

- *The investigator will have the responsibility to review the AE reported by the PA and reconcile with the AE/SAE reported in the eCRF. In case of discrepancy between the AE/SAE reported through the PA and the AE/SAE reported in the eCRF, the Investigator will have to contact the subject to request more information regarding the reported AE/SAE and correct the eCRF, if needed (see Section 8).*
- *The Investigator will have to assess whether the AE/SAE reports should be submitted within eCRF according to protocol requirements (see Section 8).*
- *Each investigator site will have to track and document the AE/SAE reconciliation.*

Any AE linked to other GSK vaccine/product must be reported to Vaccines Clinical Safety and Pharmacovigilance (VCSP) Department according to spontaneous reporting process. VCSP will process such AE/SAE (linked to marketed products) according to standard processes.

GlaxoSmithKline Biologicals SA	
Vaccines R &D Protocol Amendment 3	
eTrack study number and Abbreviated Title	204486 (ZOSTER-056)
IND number	BB-IND-13857
EudraCT number	2015-000965-30
Amendment number:	Amendment 3
Amendment date:	30 May 2017
Co-ordinating author:	PPD [redacted], Scientific Writer
Rationale/background for changes:	

 • This country specific protocol amendment was developed in order to remove the Voice of the Patient (VoP) initiative text from Section 12.3 since this initiative was not adopted in Japan. • This is a country specific administrative change for the US since the back-up study contact telephone number for reporting SAEs, pregnancies and pIMDs in the US was removed from Section 8.4.2. This US telephone number, which was originally provided to the US sites as a courtesy, became inactivated over the course of the study and the US Fax number is retained as the back-up study contact number for reporting SAEs, pregnancies and pIMDs. 	

Amended text has been included in *bold italics* and deleted text in ~~strikethrough~~ in the following sections:

LIST OF ABBREVIATIONS

- ~~PA:~~ ~~Polling Agency~~
- ~~VCSP:~~ ~~Vaccines Clinical Safety and Pharmacovigilance~~

Section 8.4.2 Contact information for reporting serious adverse events, pregnancies and pIMDs

Study Contact for Reporting SAEs, pIMDs and pregnancies
Back-up Study Contact for Reporting SAEs, pIMDs and pregnancies
24/24 hour and 7/7 day availability:
GSK Biologicals Clinical Safety & Pharmacovigilance
US sites only:
Fax: PPD [redacted] Tel: PPD [redacted]

12.3. Requirements for Japan

~~Voice of the Patient (VoP) Initiative~~

~~Subjects who are participating in the Zoster 056 study will be invited for a qualitative survey conducted by Polling Agency (PA) to better understand their own experience after the administration of HZ/su vaccine and what impact it may have had on their daily life, their perception of HZ/su and stated willingness to receive additional dose.~~

~~Contact details of the PA will be provided to the subjects by the investigators. Subjects who are willing to participate in this survey, can contact the PA at all stages during the study after the first, second dose and also when full vaccination course was not completed.~~

~~Participation in the survey will be optional and will not impact subject's participation in the study.~~

~~Results of this research as well as proposal, interviews and market research material (questionnaire) are for internal use only and will not be published.~~

~~The survey is likely to elicit safety information and robust safety reporting process will be followed.~~

~~Safety reporting process:~~

~~Adverse Event (AE) Reporting:~~

~~Any AE linked to the HZ/su vaccine reported by the interviewees must be reported by the PA to the trial investigator within 24 hours of initial receipt (or next working day if over a weekend or a national holiday).~~

~~Investigator's responsibilities are as follows:~~

- ~~• The investigator will have the responsibility to review the AE reported by the PA and reconcile with the AE/SAE reported in the eCRF. In case of discrepancy between the AE/SAE reported through the PA and the AE/SAE reported in the eCRF, the Investigator will have to contact the subject to request more information regarding the reported AE/SAE and correct the eCRF, if needed (see Section 8).~~
- ~~• The Investigator will have to assess whether the AE/SAE reports should be submitted within eCRF according to protocol requirements (see Section 8).~~
- ~~• Each investigator site will have to track and document the AE/SAE reconciliation.~~

~~Any AE linked to other GSK vaccine/product must be reported to Vaccines Clinical Safety and Pharmacovigilance (VCSP) Department according to spontaneous reporting process. VCSP will process such AE/SAE (linked to marketed products) according to standard processes.~~

1. DOCUMENT HISTORY

Date	Description	Protocol Version
26-FEB-2019	Final version Please note: As the SAP has been started long back (19Dec2017) and reviewed also but was not finalized due to study team change and delay in the outcome of the Shingrix After Action Review (AAR) post Type C meeting with CBER which was required to be implemented in this SAP, the old template of the SAP has been used. This has been agreed by Lead Statistician.	Amendment 3 Final: 30-MAY-2017

2. STUDY DESIGN

*Could be a visit or a phone contact.

i.e. 12 months post dose 2

n: number of subjects

Vacc: vaccination

SFU: Safety follow-up

- Experimental design: Phase IIIB open-label, non-randomised, multi-centric, multi-country cross-vaccination study, with a single group.
- Duration of the study: Approximately 14 months. Each subject will be followed for safety approximately 12 months after the second vaccine dose
 - Epoch 001: Primary starting at Visit 1 (Month 0) and ending at final phone contact (Month 14, i.e. 12 months post dose 2)
- Study groups:

Table 1 Study groups and epochs foreseen in the study

Study Groups	Number of subjects	Age (Min – Max)	Epochs
			Epoch 001
HZ/su Group	max 14,550	> 50 YOA	x

Table 2 Study groups and treatment foreseen in the study

Treatment name	Vaccine/Product name	Study Groups
HZ/su	VZV gE	HZ/su Group
	AS01 _B	

- Control: uncontrolled.
- Vaccination schedule: 0, 2 months.
- Treatment allocation: non-randomised.
- Blinding: open-label.

Table 3 Blinding of study epochs

Study Epochs	Blinding
Epoch 001	open

- Sampling schedule: no sampling.
- Type of study: self-contained.
- Data collection: electronic Case Report Form (eCRF).

3. OBJECTIVES

3.1. Primary objective

- To evaluate the safety, in terms of unsolicited Adverse Events (AEs), Serious Adverse Events (SAEs) and pIMD in all subjects, following administration of each dose of the HZ/su vaccine.

3.2. Secondary objective

- To evaluate the incidence of suspected HZ episodes (self-reported or medically diagnosed) during the entire study period.

4. ENDPOINTS

4.1. Primary endpoints

- Occurrence of unsolicited AEs.
 - Occurrence, intensity and relationship to vaccination of unsolicited AEs during 30 days (Days 0-29) after each vaccination, according to the Medical Dictionary for Regulatory Activities (MedDRA) classification.
- Occurrence of SAEs.
 - Occurrence and relationship to vaccination of all SAEs from Month 0 until study end (Month 14, i.e. 12 months post dose 2).
- Occurrence of AEs of special interest.
 - Occurrence of any pIMDs from Month 0 until study end (Month 14, i.e. 12 months post dose 2).

4.2. Secondary endpoints

- Occurrence of suspected HZ cases.
 - Occurrence of suspected HZ cases from Month 0 to study end.

5. ANALYSIS SETS

5.1. Definition

5.1.1. Total Vaccinated Cohort

This study will collect only safety data. The statistical analysis of the safety endpoints will be based on the Total Vaccinated Cohort (TVC); hence no according to protocol (ATP) cohorts are defined for the purpose of statistical analysis.

The Total vaccinated cohort will include all subjects with at least one HZ/su vaccine administration documented for whom data are available:

- A safety analysis based on the Total vaccinated cohort will include all vaccinated subjects.

5.2. Criteria for eliminating data from Analysis Sets

5.2.1. Elimination from Total Vaccinated Cohort (TVC)

Code 900 (invalid informed consent or fraud data) and code 1030 (Study vaccine not administered at all) will be used for identifying subjects eliminated from Total Vaccinated Cohort.

5.2.1.1. Excluded subjects

A subject will be excluded from the TVC analysis under the following conditions:

Code	Condition under which the code is used
900	Invalid informed consent and fraud data (Subjects receiving a code 900 should not receive any other elimination codes)
1030	Study vaccine not administered at all (Subjects receiving a code 1030 should not receive any other elimination codes)

6. STATISTICAL ANALYSES

Note that standard data derivation rules and statistical methods are described in Section 11 and will not be repeated below.

6.1. Demography

6.1.1. Analysis of demographics/baseline characteristics planned in the protocol

Demographic characteristics (age at first study vaccination in years, gender), withdrawal status will be summarised using descriptive statistics:

- Frequency tables will be generated for categorical variable such as centre.
- Mean, median, standard deviation will be provided for continuous data such as age, in Years, at vaccination in the current study.

6.1.2. Additional considerations

- Demographic characteristics will also be tabulated by age sub-group at vaccination in the ZOSTER-056 (50-59, 60-69, 70-79 and ≥ 80 YOA).
- List of subjects withdrawn from vaccination with reason for withdrawal will be presented.
- The following table will be performed for web-disclosure:
 - Percentage of Enrolled subjects by country will be tabulated,
 - Percentage of Enrolled subjects in the following age categories ≤ 64 , 65-84, ≥ 85 will be tabulated.

6.2. Exposure

6.2.1. Analysis of exposure planned in the protocol

Not applicable.

6.2.2. Additional considerations

The number of doses administered will be tabulated overall and by age sub-group at vaccination in the ZOSTER-56 (50-59, 60-69, 70-79 and ≥ 80 YOA).

6.3. Analysis of safety

6.3.1. Analysis of safety planned in the protocol

The analysis for safety will be based on the TVC.

All analysis will be performed overall and by age sub-group at vaccination in the ZOSTER-056 (50-59, 60-69, 70-79 and ≥ 80 YOA).

When appropriate, tabulations will be presented overall and by time of occurrence related to last vaccination (e.g. using windows such as Days 0-29 and more than 30 days post-vaccination).

The results for the analysis of safety will be tabulated as follows:

- The proportion of subjects with at least one report of an unsolicited AE during the 30-day (Days 0–29) follow-up period after each vaccination classified according to the MedDRA System Organ Class and Preferred Terms will be tabulated, with exact 95% CI.
- The same tabulation will be performed for grade 3 unsolicited AEs (including SAEs) and for unsolicited AEs with a relationship to vaccination. The proportion of AEs resulting in a medically attended visit will also be tabulated.
- Total number/percentages of doses (per dose and overall) followed by AEs during the 30 days (Days 0-29) follow-up period after each vaccination classified according to the MedDRA System Organ Class and Preferred Terms will be tabulated.
- SAEs will be described in detail in listing for the entire study period.
- Withdrawal due to AE(s) and SAE will be described in detail in listing for the entire study period.
- Number of subjects with pIMDs will be tabulated according to the MedDRA System Organ Class and Preferred Terms for the period during first vaccination up to 30 days post second vaccine dose, after 30 days post second vaccine dose to study end and from first vaccination to study end.

6.3.2. Additional considerations

Following additional analyses will be performed:-

1. Number and percentage of subjects with at least one report of a grade 3 non-serious unsolicited AE during the 30-day (Days 0–29) follow-up period after each vaccination classified according to the MedDRA System Organ Class and Preferred Terms will be tabulated, with exact 95% CI.

2. Number and percentage of subjects reporting at least one SAE/ pIMD classified according to the MedDRA System Organ Class and Preferred Terms will be tabulated, with exact 95% CI with onset day of SAE during the time interval during study start to 30 days post 2nd vaccine dose, after 30 days post 2nd vaccine dose till study end and from study start till study end.
3. Number and percentage of subjects with fatal SAEs, classified by MedDRA Primary System Organ Class and Preferred Term will be presented with exact 95% CI in two ways:-
 - With onset of fatal SAE during the period starting from first vaccination to 30 days post last vaccination dose, after 30 days post last vaccination dose to study end and from first vaccination to study end
 - Who died during the period starting from first vaccination to 30 days post last vaccination dose, after 30 days post last vaccination dose to study end and entire study period.
4. Number and percentage of subjects reporting the occurrence of unsolicited adverse events classified by MedDRA Primary System Organ Class and Preferred Term within the 30-day (Days 0-29) post-vaccination period will also be presented, overall and by age sub-group with exact 95% CI on Total Vaccinated Cohort considering only subjects with a confirmed HZ episode during Zoster-006/022. The same tabulation will be performed for grade 3 unsolicited AEs and for unsolicited AEs with a relationship to vaccination.
5. Number and percentage of subjects reporting the occurrence of serious adverse event and pIMD, classified by MedDRA Primary System Organ Class and Preferred Term from first vaccination until study end will also be presented with exact 95% CI on Total Vaccinated Cohort considering only subjects with a confirmed HZ episode during Zoster-006/022.
6. List of subjects withdrawn from vaccination with reason for withdrawal will be presented from first vaccination until study end.
7. Listing of potential Immune-Mediated Diseases (pIMDs) reported as identified by predefined list of preferred terms and/or by investigator assessment from first vaccination until study end will be presented. Listing of the subjects who died will also be generated for the entire study period.
8. The unsolicited adverse events experienced within 30 days (Day 0-29) by subjects post receipt of only adjuvant will be presented in the listing.
9. Number and percentage of subjects with Past/Current pre-existing medical conditions by SOC and PT will be presented.

6.4. Analysis of suspected HZ incidence

6.4.1. Analysis of suspected HZ incidence planned in Protocol

1. The number of suspected HZ cases will be tabulated on TVC.

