5.6.15. Recording of suspected HZ episodes**5.6.15.1. Suspected HZ**

A suspected case of HZ is defined as a new rash characteristic of HZ (e.g., unilateral, dermatomal and accompanied by pain broadly defined to include allodynia, pruritus or other sensations).

A diagnosis of suspected HZ will be based upon investigator or the attending physician judgment. The occurrence of suspected HZ will be reported as an AE/SAE, as appropriate. The reporting period for cases of suspected HZ will be from Day 0 to study end.

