11. ANNEX 1 STANDARD DATA DERIVATION RULES AND STATISTICAL METHODS

11.1. Statistical Method References

The exact two-sided 95% CIs for a proportion within a group will be the Clopper-Pearson exact CI [Clopper CJ, Pearson ES. The use of confidence or fiducial limits illustrated in the case of binomial. *Biometrika*. 1934;26:404-413].

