n/% = number/percentage of doses with the symptom

95% CI= exact 95% confidence interval; LL = Lower Limit, UL = Upper Limit

Template 20 Global summary of <grade 3> <non-serious><unsolicited adverse events> <with causal relationship to vaccination> <with medically attended visit> reported within the 30-day (Days 0-29) post-vaccination period (Total Vaccinated Cohort)

	HZ/su
Number of subjects with at least one unsolicited symptom reported	
Number of doses followed by at least one unsolicited symptom	
Number of unsolicited symptoms classified by MedDRA Preferred Term*	
Number of unsolicited symptoms reported**	

HZ/su = Herpes Zoster subunit vaccine

* Symptoms reported by a subject after a given dose and classified by the same Preferred Term are counted once

** Symptoms reported by a subject after a given dose and classified by the same Preferred Term and the same start date of the event, are counted once

Template 21 Number and percentage of subjects reporting the occurrence of <potential Immune-Mediated Diseases> <serious adverse events> classified by MedDRA Primary System Organ Class and Preferred Term <with causal relationship to vaccination> reported <from first vaccination up to 30 days post last vaccination dose> <after 30 days post last vaccination dose up to study end><from first vaccination until study end > (<Total Vaccinated Cohort, Total Vaccinated Cohort - confirmed HZ episode during Zoster-006/022>)

		HZ/su N =				
					95% CI	
Primary System Organ Class (CODE)	Preferred Term (CODE)	n*	n	%	LL	UL
At least one symptom						
Each SOC	At least one PT related to the corresponding SOC					
	Each PT					

HZ/su = Herpes Zoster subunit vaccine group

At least one symptom = at least one symptom experienced (regardless of the MedDRA Preferred Term)

N = number of subjects with the administered dose

n/%= number/percentage of subjects reporting the symptom at least once

95% CI = exact 95% confidence interval; LL = Lower Limit, UL = Upper Limit

n* = number of events reported (only required for CTRS posting)

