Group	Sub No.	Sex	Country	Race	Age at Onset (Year)	Verbatim	Preferred term	Primary System Organ Class	MED type	Dose prior to onset of fatal SAE	Days between onset of fatal SAE and previous dose	Dose prior to death	Days between death and previous dose	SAE Duration	SAE Causality
HZ/su	X1								HO						
	X2								HO						
	X3								HO						

HZ/su = Herpes Zoster subunit vaccine
 No Group= Enrolled not vaccinated
 MED = Medical Advice type (HO: hospitalisation, ER: emergency room visit, MD: medical practice visit)

Template 35 Unsolicited adverse events classified by MedDRA Primary System Organ Class and Preferred Term within the 30-day (Days 0-29) post-vaccination period including number of events - SAE excluded (Total Vaccinated Cohort)

Primary System Organ Class (CODE)	Preferred Term (CODE)	HZ/su N =		
		n*	N	%
At least one symptom				
<each SOC>	<each PT term>			

HZ/su = Herpes Zoster subunit vaccine

At least one symptom = at least one symptom experienced (regardless of the MedDRA Preferred Term)

N = number of subjects with at least one administered dose

n* = number of events reported

n/% = number/percentage of subjects reporting the symptom at least once

Template 36 Number (%) of subjects with serious adverse events from first vaccination until study end including number of events reported (Total Vaccinated Cohort)

Type of Event	Primary System Organ Class	Preferred Term (CODE)	HZ/su N =		
			n*	N	%
SAE	At least one symptom				
	<each SOC>	<each PT term>			
Related SAE	At least one symptom				
	<each SOC>	<each PT term>			
Fatal SAE	At least one symptom				
	<each SOC>	<each PT term>			
Related fatal SAE	At least one symptom				
	<each SOC>	<each PT term>			

HZ/su = Herpes Zoster subunit vaccine group

N = number of subjects with the administered dose

n* = number of events reported

n/% = number/percentage of subjects reporting the event at least once

Template 37 Number and percentage of suspected HZ episodes (Total Vaccinated Cohort)

Categories	HZ/su N =	
	n	%
HZ episode		
Suspected HZ episode only		
Confirmed HZ episode		

HZ/su = Herpes Zoster subunit vaccine

N = total number of subjects

n/% = number / percentage of subjects in a given category

HZ episode: number of subjects with at least one suspected episode

Suspected HZ episode only: Suspected HZ episode not confirmed by the Investigator/Delegate

Confirmed HZ episode: Suspected HZ episode confirmed by the Investigator/Delegate

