Template 38 Number and percentage of suspected HZ episodes considering only subjects who had a confirmed HZ episode during Zoster-006/022 (Total Vaccinated Cohort)

Categories	HZ/su N =	
	n	%
HZ episode		
Suspected HZ episode only		
Confirmed HZ episode		

HZ/su = Herpes Zoster subunit vaccine

N = total number of placebo subjects from Zoster-006/022 (TVC) with a confirmed HZ episode during Zoster-006/022 vaccinated in this study

n/% = number / percentage of subjects in a given category

HZ episode: number of subjects with at least one suspected episode

Suspected HZ episode only: Suspected HZ episode not confirmed by the Investigator/Delegate

Confirmed HZ episode: Suspected HZ episode confirmed by the Investigator/Delegate

Template 39 Number and percentage of suspected HZ episodes - by age sub-group (Total Vaccinated Cohort)

Categories	[each age sub-group]* N=		Total N =	
	n	%	N	%
HZ episode				
Suspected HZ episode only				
Confirmed HZ episode				

*Age sub-group is based on subject's age at first vaccination

50-59YOA = Subjects aged 50-59 years

60-69YOA = Subjects aged 60-69 years

70-79YOA = Subjects aged 70-79 years

≥80YOA = Subjects aged 80years and over

HZ/su = Herpes Zoster subunit vaccine

N = total number of subjects

n/% = number / percentage of subjects in a given category

HZ episode: number of subjects with at least one suspected episode

Suspected HZ episode only: Suspected HZ episode not confirmed by the Investigator/Delegate

Confirmed HZ episode: Suspected HZ episode confirmed by the Investigator/Delegate

Template 40 Number and percentage of suspected HZ episodes considering only subjects who had a confirmed HZ episode during Zoster-006/022 - by age sub-group (Total Vaccinated Cohort)

Categories	[each age sub-group]* N=		Total N=	
	n	%	N	%
HZ episode				
Suspected HZ episode only				
Confirmed HZ episode				

*Age sub-group is based on subject's age at first vaccination

50-59YOA = Subjects aged 50-59 years

60-69YOA = Subjects aged 60-69 years

70-79YOA = Subjects aged 70-79 years

≥80YOA = Subjects aged 80years and over

HZ/su = Herpes Zoster subunit vaccine

N = total number of placebo subjects from Zoster-006/022 (TVC) with a confirmed HZ episode during Zoster-006/022 and vaccinated in this study

n/% = number / percentage of subjects in a given category

HZ episode: number of subjects with at least one suspected episode

Suspected HZ episode only: Suspected HZ episode not confirmed by the Investigator/Delegate

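### The tables for the only secondary endpoint, suspected HZ, give n and % with no confidence interval and no person-time, although the main AE, SAE, pIMD and fatal-SAE tables carry exact 95% CIs

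*SAP*

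**What the plan says.** The SAP's only secondary objective (3.2, the same in protocol 2.2) is "To evaluate the incidence of suspected HZ episodes (self-reported or medically diagnosed) during the entire study period". The matching endpoint in SAP 4.2 is the occurrence of suspected cases from Month 0 to study end.

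For the analysis, SAP 6.4.1 says "The number of suspected HZ cases will be tabulated on TVC". This follows protocol 10.8, which also plans a number only. SAP 6.4.2 repeats the analysis in subjects with a confirmed HZ episode in ZOSTER-006/022 and adds a listing.

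Templates 37-40 have columns n and % and nothing else. The first row is explained by the footnote "HZ episode: number of subjects with at least one suspected episode". In Template 38 the denominator is "N = total number of placebo subjects from Zoster-006/022 (TVC) with a confirmed HZ episode during Zoster-006/022 vaccinated in this study".

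Elsewhere the SAP asks for intervals. Sections 6.3.1 and 6.3.2 call for exact 95% CIs for unsolicited AEs, SAEs, pIMDs and fatal SAEs. For SAEs and pIMDs in the subset with earlier confirmed HZ, 6.3.2 item 5 says results "from first vaccination until study end will also be presented with exact 95% CI on Total Vaccinated Cohort". The corresponding shells have LL and UL columns; the footnote of Template 19, for example, reads "95% CI= exact 95% confidence interval; LL = Lower Limit, UL = Upper Limit". The method is fixed in 11.1: "The exact two-sided 95% CIs for a proportion within a group will be the Clopper-Pearson exact CI".

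**The concern.** The endpoint is named as an incidence, yet no measure of its precision is planned, in the text of 6.4 or in the tables. If an age sub-group or the prior-HZ subset has few cases or none, the report will show a bare 0 or 0.1%, and the reader is not told what incidence remains compatible with the data. For SAEs and pIMDs in the same subjects the SAP does give that information. The prior-HZ subset is where a bare zero is most easily over-read, because protocol 1.1 says that efficacy against recurrent HZ had not been evaluated.

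There is a smaller second point. Suspected HZ is handled as an adverse event (protocol 5.6.15.1: "The occurrence of suspected HZ will be reported as an AE/SAE, as appropriate"). Under the AE convention of protocol 10.5 and SAP 11.2.4, a subject who withdraws without reporting an episode stays in N as event-free, so the percentage slightly understates incidence. A percentage over about 14 months is also not in the per-1000-per-year form that protocol 1.1 uses for HZ.

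**Working it through.** The documents give no precision or sample-size figure for this endpoint (protocol 10.3 calculates none), so there is no stated number to reproduce. The check has two parts.

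**1. Which tables carry an interval**

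| Content | Templates | Exact 95% CI | Person-time |
|---|---|---|---|
| Unsolicited AEs by SOC/PT, subjects and doses | 18, 19, 25, 26 | yes | no |
| SAEs and pIMDs by SOC/PT | 21, 28 | yes | no |
| Fatal SAEs by SOC/PT | 22, 29 | yes | no |
| Global AE summaries; tables with event counts | 20, 27, 35, 36 | no | no |
| Suspected HZ | 37, 38, 39, 40 | no | no |

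So 8 of 8 main SOC/PT safety tables have an interval and 0 of 4 HZ tables do. No table uses person-time, so its absence is not peculiar to HZ.

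**2. What the missing interval would show**

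Inputs:
- N = 3349 (age 70-79) and N = 2109 (80 and over), from SAP section 9.
- Follow-up from the optimal intervals in protocol Table 5: 60 + 365 = 425 days, and 425/365.25 = 1.1636 years.
- Assumed, because the documents do not give them: case counts of 0 and 3; withdrawals of 5% to 20% at mid follow-up; 100 to 500 subjects in the prior-HZ subset.

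*Proportion (Clopper-Pearson).* For x cases in N, the lower limit is the 2.5% quantile of Beta(x, N−x+1) (0 if x = 0) and the upper limit is the 97.5% quantile of Beta(x+1, N−x). For x = 0 the upper limit is 1 − 0.025^(1/N).

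| Group | 0 cases: upper limit | 3 cases: % (95% CI) |
|---|---|---|
| 70-79, N=3349 | 0.110% | 0.090% (0.018-0.262) |
| 80 and over, N=2109 | 0.175% | 0.142% (0.029-0.415) |
| Prior HZ, assumed N=100 | 3.62% | – |
| Prior HZ, assumed N=500 | 0.74% | – |

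Under the one-decimal rule of SAP 11.3, both 3-case results print as 0.1%. One case in 2109 (0.047%) prints as 0.0%, although its upper limit is 0.26%.

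*Rate (exact Poisson).* For x subjects in T person-years, the lower limit is chi-square(0.025; 2x)/(2T) (0 if x = 0) and the upper limit is chi-square(0.975; 2x+2)/(2T). With full follow-up:

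- 70-79: T = 3349 × 1.1636 = 3,897. Three cases: 3/3,897 = 0.77 per 1000 person-years, limits 1.237/(2 × 3,897) and 17.535/(2 × 3,897), that is 0.16-2.25. Zero cases: upper limit 7.378/(2 × 3,897) = 0.95.
- 80 and over: T = 2109 × 1.1636 = 2,454. Three cases: 1.22 (0.25-3.57). Zero cases: upper limit 1.50.

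*Effect of withdrawal.* If a fraction w leaves at mid follow-up, person-time is multiplied by 1 − w/2, which is 0.975 at 5% and 0.90 at 20%.

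- 70-79: T falls to 3,799 or 3,507, and the 3-case rate becomes 0.79 or 0.86.
- 80 and over: T falls to 2,393 or 2,209, and the rate becomes 1.25 or 1.36.

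These shifts lie well inside the intervals above, so sampling error outweighs incomplete follow-up unless withdrawal is high.

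**The case against.** **The plan keeps to the protocol and everything is descriptive.** Protocol 10.8 asks for a count, the SAP adds percentages, sub-groups and a listing, and there is no hypothesis or power claim. This is true, and it is why the point concerns reporting rather than an error in a stated figure. It does not explain the gap: the AE, SAE, pIMD and fatal-SAE tables are equally descriptive and have intervals, and the SAP already adds analyses that the protocol did not plan.

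**HZ is secondary, and other tables also lack intervals.** Templates 20, 27, 35 and 36 do lack them. For AEs and SAEs, however, the intervals appear in companion tables. HZ has no companion table.

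**Suspected HZ is already covered as an AE or SAE.** Only in part. The AE tables stop at Day 29 after each dose and the SAE tables hold serious episodes only. Non-serious episodes after Day 29 are in neither, and the endpoint from Month 0 to study end never receives an interval.

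**Incidence need not mean person-time.** SAP 11.2.2 defines incidence per dose as a proportion. That definition covers doses, not this endpoint. Still, SAEs and pIMDs have no rates, no comparison with background rates is planned, and the calculation shows a small effect of withdrawal. Protocol 10.5 also allows the analysis plan to be reassessed if non-compliance with event reporting is significant. The rate is thus an improvement and not the repair of an inconsistency.

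**A reader can compute the interval from n and N.** Correct, but the study report would not show it. It is also fair that, at one decimal, the 3-case intervals would print only as 0.0-0.3 and 0.0-0.4.

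**The wording points are mostly handled.** The footnotes of Template 37 already separate confirmed from unconfirmed episodes, and SAP section 13 lets titles be adapted. Those changes are clerical.

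**Conclusion.** The concern holds. The single secondary endpoint is the one main safety outcome summarised without any interval, and the omission is in the text of SAP 6.4 as well as in the shells. At the sub-group sizes the SAP gives, zero cases would leave upper limits of 0.11% (70-79) and 0.17% (80 and over) unstated. In a prior-HZ subset of 100 to 500 subjects the unstated limit would be 3.6% to 0.7%. The sizes 3349 and 2109 come from the SAP; the case counts, withdrawal fractions and subset size are assumptions for illustration.

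The effect is on what the report tells its reader. No hypothesis test, power figure or primary safety analysis changes. The change should be made, but it is not critical to the trial's main conclusions.

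**What to change.** In SAP 6.4.1, 6.4.2 and Templates 37-40:

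- Keep n and %, and add LL and UL columns with the Clopper-Pearson 95% CI already defined in 11.1.
- Add the rate of subjects with a first suspected episode per 1000 person-years with an exact Poisson 95% CI, overall, by age sub-group and in the prior-confirmed-HZ subset. Person-time runs from the first dose to the earliest of first suspected episode, death, withdrawal or last contact. Put the chi-square formula shown in the working into 11.1.
- In 11.2.4, state that the HZ episode row counts subjects with at least one suspected episode, confirmed or not, and that cases confirmed by the investigator or delegate are a subset. The present text there says that a suspected episode must be confirmed, which does not fit the unconfirmed row in Template 37.
- Retitle Templates 37-40 so that they refer to subjects with suspected HZ episodes.
- Optional: two decimals in these four tables, and a row for the total number of episodes.

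The cost is SAP wording in three places, four templates and one follow-up variable derived from dates already collected. The tables become slightly larger, and the rate averages over the time before and after the second dose. No protocol amendment or change in conduct is needed.
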